## 3. **Abstract:**

Mobility is a critical factor in the maintenance of independence and quality of life of older adults. Chronic musculoskeletal pain contributes to mobility disability disproportionately among older adults. Current treatments for pain and functional decline are often ineffective and add to heightened risks of polypharmacy in older adults. As such, nutritional interventions can play a significant role in promoting health and longevity, managing pain, and enhancing physical function in older adults. Omega ( $\omega$ )-3 polyunsaturated fatty acids (PUFAs) are essential nutrients that are well recognized for their anti-inflammatory and cardioprotective benefits, as well as their analgesic and anti-nociceptive properties. Most American adults do not meet the recommendations for  $\omega$ -3 intakes, particularly eicosapentaenoic acid (EPA) and docosahexaenoic acid (DHA), found primarily in seafood. Due to competing pathways, an elevated  $\omega$ -6 to  $\omega$ -3 ratio contributes to an overproduction of pro-inflammatory eicosanoids and the development of chronic diseases. A high  $\omega$ -6: $\omega$ -3 ratio is associated with higher chronic pain prevalence and increased pain severity. Additionally,  $\omega$ -3 PUFAs may play a role in the preservation of muscle and physical function in older adults. Low levels of  $\omega$ -3s in blood are associated with reduced muscle strength, slower gait speed, and mobility disability among older adults.

Considered largely safe and cost-effective,  $\omega$ -3 supplementation may be crucial to increasing the intake of these essential nutrients and achieving optimal levels among older adults. Although the use of EPA and DHA has been incorporated into several guidelines, a scarcity of data has prevented the development of strong recommendations on the use of  $\omega$ -3 supplementation for the maintenance of physical function in older adults, particularly those with chronic musculoskeletal pain. Krill oil has been recently proposed as an advantageous alternative to traditional fish oil supplements, due to a greater bioavailability of EPA and DHA and additional bioactive compounds. The goal of this pilot study is to assess the feasibility of a 3-month randomized controlled trial to determine the effectiveness of krill oil supplementation on pain and physical function in older adults with chronic musculoskeletal pain. We will enroll 40 older adults ( $\geq 60$  years) who will be randomly assigned to 4 g krill oil (1,288 mg/d EPA+DHA, 0.45 mg astaxanthin,

320 mg choline) daily or matched placebo (mixed lipids without EPA and DHA). We will determine the impact of krill oil supplementation on the omega-3 index (%EPA+DHA in erythrocytes), the  $\omega$ -6/ $\omega$ -3 ratio, and inflammatory biomarkers in blood, and obtain preliminary evidence of its impact on pain and physical function in older adults. The findings of this pilot will inform a future fully-powered randomized controlled trial by assessing the feasibility and acceptability of krill oil supplementation among older U.S. adults with chronic musculoskeletal pain.

#### 4. Background:

Mobility limitations are experienced by about a third of U.S. older adults, affecting their independence and quality of life. Considered a key hallmark of functional aging, mobility limitations are indicative of physical decline, predicting disability and mortality. Chronic musculoskeletal pain, similarly prevalent among older adults, contributes significantly to mobility limitations, functional decline, and disability. As such, the intersection of chronic pain and physical function represents an important target for interventions. However, pain management is particularly challenging and often ineffective in older adults, as are interventions to prevent or delay functional decline. With increased risks of polypharmacy in older adults, there is a need for non-pharmacological approaches for pain and physical function in older adults.

Considered generally safe and cost-effective, supplementation with omega ( $\omega$ )-3 polyunsaturated fatty acids (PUFAs) has been proposed for various age-related conditions, including chronic pain, cognitive health, and functional decline. Despite being essential nutrients,  $\omega$ -3s are inadequately consumed by most older U.S. adults. In particular, eicosapentaenoic acid (EPA) and docosahexaenoic acid (DHA) are recognized for their anti-inflammatory properties and potential health benefits in aging. Omega-3s could also reduce neuropathic and nociceptive pain by modulating peripheral and central sensitization. In contrast, dietary  $\omega$ -6 PUFAs are abundant and contribute to an overproduction of pro-inflammatory eicosanoids. An elevated  $\omega$ -6: $\omega$ -3 ratio is associated with higher chronic pain prevalence and increased pain severity. Moreover, low serum  $\omega$ -3 is associated with reduced muscle strength, slower gait speed, and mobility disability among older adults.

Of the various sources of  $\omega$ -3s, krill oil has been recently proposed as an advantageous alternative to traditional fish oil supplements. Krill oil offers greater bioavailability of EPA+DHA and is a naturally occurring source of additional bioactive compounds, such as astaxanthin, a potent anti-inflammatory/antioxidant. Krill oil supplementation has been shown to reduce self-reported pain intensity, mostly in middle-aged adults and samples that do not adequately represent the older U.S. population. To our knowledge, only one study has examined the effects of krill oil on functional outcomes in older adults. Noteworthy, this study found significant improvements in both muscle strength and function in generally healthy older adults. However, no study to date has examined the effects of krill oil specifically on older U.S. adults with chronic musculoskeletal pain.

**4.1. Chronic pain impairs physical function in older adults:** Chronic musculoskeletal pain is the greatest cause of disability worldwide, and older adults are especially vulnerable to chronic pain and painful conditions. Over a third of older U.S. adults suffer from chronic pain (i.e., pain that persists for >3 months). Furthermore, older adults are highly susceptible to the detrimental impacts of chronic pain, including functional impairments and disability, as well as chronic diseases and psychiatric conditions that can be exacerbated by chronic pain. Alarming, the prevalence of chronic pain has been on the rise. As the number and proportion of older adults continue to grow to comprise nearly a quarter of the U.S. population by 2060, the chronic pain burden in this population represents a significant challenge to public health and health systems.

**4.2. Omega-3 fatty acids are essential nutrients** that must be obtained through the diet since humans cannot synthesize them. More specifically, eicosapentaenoic acid (EPA) and docosahexaenoic acid (DHA) are conditionally essential since they can be synthesized from dietary alpha-linolenic acid (ALA); however, the conversion is limited in humans. ALA is found mainly in plants and EPA/DHA are found mainly in seafood. The majority of older adults in the U.S. do not meet the recommendations for  $\omega$ -3 PUFA intake and less than 2% have EPA+DHA blood concentrations associated with low cardiovascular disease risk.

**4.3. Omega-3s modulate pain:**  $\omega$ -3 PUFAs are recognized for their anti-inflammatory and anti-oxidative properties, leading to increased interest in their role and utilization in inflammatory and musculoskeletal conditions. EPA and DHA generate prostaglandins, leukotrienes, and D- and E-series resolvins, which have potent anti-inflammatory effects through cyclooxygenase (COX) and lipoxygenase (LOX) activity (**Fig. 2**). Additionally,  $\omega$ -3 fatty acids exert analgesic and anti-nociceptive activity, influencing pain sensitivity via peripheral and central nerve signaling. As such,  $\omega$ -3 PUFAs can have a positive impact on joint pain associated with conditions such as arthritis. Indeed, a recent meta-analysis of nine randomized controlled trials (N=2,070) found that  $\omega$ -3 supplementation resulted in significant improvements in osteoarthritis pain and joint function compared to placebo, with no serious adverse events.

**4.4. The  $\omega$ -6/ $\omega$ -3 ratio influences inflammatory pathways:** Both  $\omega$ -6 and  $\omega$ -3 PUFAs are essential nutrients with beneficial properties as compared to saturated fats. In contrast to  $\omega$ -3 PUFAs,  $\omega$ -6s contribute to the formation of pro-inflammatory lipid mediators necessary as part of a healthy inflammatory response. Yet, whereas an  $\omega$ -6: $\omega$ -3 ratio of 4:1 to 1:1 is considered optimal for human health, the typical Western diet has resulted in a ratio of 15:1 or greater. Due to a competing pathway of long-chain PUFA synthesis enzymes (**Fig. 1**), an imbalance of  $\omega$ -6 to  $\omega$ -3 PUFAs results in the overproduction of pro-inflammatory signaling

[figure not shown]

Figure 1. PUFA metabolism, Curr Surg Rep 4,28(2016)

molecules. Given the abundance of  $\omega$ -6 PUFAs in the Western diet and that these possess health benefits as compared to saturated fats, supplementation with  $\omega$ -3 PUFAs is now thought to be essential to achieve an adequate  $\omega$ -6: $\omega$ -3 ratio.

**4.5. Omega-3s may preserve physical function:**  $\omega$ -3 supplementation may be beneficial for preserving age-related loss of muscle mass, strength, and physical function. Although not fully elucidated, potential mechanisms for these beneficial effects include anti-catabolic and anabolic properties, improved insulin sensitivity, preservation of mitochondrial function, and neuroprotective effects. Recent meta-analyses of  $\omega$ -3 supplementation trials have shown improvements in lower-body strength and function in older adults.

**4.6. Krill oil is considered a superior source of  $\omega$ -3s** as compared to fish oil and is a naturally occurring source of additional bioactive compounds that may enhance its benefits. Krill (*Euphausia superba*) are small marine crustaceans. While krill oil contains similar amounts of EPA+DHA as other common fish oils,  $\omega$ -3 PUFAs in krill oil are mainly found in the form of **phospholipids**, whereas in fish oil they are mainly found as triglycerides. Because phospholipids are components of cell membranes, this distinction is thought to increase the bioavailability of  $\omega$ -3 PUFAs in krill oil. Indeed, in healthy volunteers, comparable rises in plasma  $\omega$ -3 levels were achieved with krill oil and fish oil supplementation, despite a nearly 30% lower EPA+DHA content in krill oil. When similar EPA+DHA contents are provided, krill oil demonstrates a higher 72-hour bioavailability compared to fish oil.

**4.7. Additional bioactive compounds in krill:** Krill oil also naturally contains **astaxanthin**, a reddish-orange xanthophyll carotenoid with powerful anti-inflammatory/antioxidant properties. As astaxanthin is primarily found in seaweeds and seafood, it is poorly consumed in the Western diet. Astaxanthin is considered a geroprotector, as it may confer several aging benefits beyond its antioxidant properties, such as by crossing the blood-brain barrier and interacting with molecular pathways that promote neurogenesis. Growing evidence from *in vitro* and *in vivo* studies suggest potential benefits of astaxanthin on several age-related conditions, including sarcopenia. Rodent models also suggest that astaxanthin may modulate inflammatory and neuropathic pain. Krill is also a natural source of phosphatidylcholine. **Choline** is an essential nutrient that is involved in several biological processes relevant to aging, such as neurotransmission, cell signaling, lipid metabolism, and homocysteine regulation. Choline is consumed at suboptimal levels by the vast majority of U.S. older adults, with fewer than 3% of adults aged  $\geq 71$  years consuming over the adequate intake level. These levels of consumption have been associated with liver disease, muscle damage, and neurological disorders. Although much of the focus around choline has centered on brain health and cognitive function, choline is also essential for skeletal muscle. Choline modulates fat and protein metabolism in muscle, decreasing fat synthesis and promoting muscle growth and function, as well as modulating inflammation, apoptosis, and autophagy. Moreover, animal models demonstrate analgesic and anti-nociceptive actions of choline via activation of  $\alpha$ -7 nicotinic acetylcholine receptors and inhibition of inflammatory pathways (i.e., HMGB1, TLR4, and NF- $\kappa$ B).

**4.8. Krill oil may reduce pain in older adults.** To date, five studies have investigated the effectiveness of krill oil supplementation on pain and function, mostly in middle-aged and non-U.S. samples. Krill oil supplementation ranged from 0.3-4 grams for a duration of 1-6 months. Of note, two studies used a krill oil-based product with added astaxanthin and hyaluronic acid. All studies found statistically significant reductions in self-reported pain intensity and functional interference. In rodent models, krill oil has outperformed fish oil in reducing clinical measures of arthritis, as well as inflammatory markers (IL-6 and TNF- $\alpha$ ) and nociceptive pain (i.e., pain that arises from actual or potential damage to non-neural tissue).

**4.9. Krill oil may improve physical function in older adults.** Of the studies mentioned above, only one included an objective assessment of physical function. No changes in a 6-minute walk were seen after 8 weeks of krill oil supplementation among mostly middle-aged adults. However, in a recent randomized controlled trial of generally healthy older adults ( $\geq 65$  y), 4 g/d krill oil supplementation for 6 months resulted in significant improvements in muscle function and size relative to placebo. Specifically, krill oil supplementation resulted in increased knee extensor maximal torque, grip strength, and vastus lateralis muscle thickness.

Despite the promising results, studies of krill oil supplementation on targeted samples of older adults with chronic musculoskeletal pain and mobility limitations with objective measures of physical function are needed.

## 5. Specific Aims:

This pilot study will assess the feasibility of a 3-month double-blinded, randomized, placebo-controlled trial to determine the effectiveness of krill oil supplementation on pain and physical function in older adults with chronic musculoskeletal pain. We will enroll 40 older adults ( $\geq 60$  years) who will be randomly assigned (1:1) to 3 months of krill oil supplementation or a matching placebo control. According to NIH guidelines for pilot studies, the proposed study will primarily assess the feasibility and acceptability of the approach. Due to small sample sizes, pilot studies cannot adequately provide evidence of safety, tolerability, or effect sizes. As such, the following aims will be accomplished:

**Specific Aim 1:** Determine the feasibility and acceptability of a double-blinded, randomized, placebo-controlled trial to investigate the effectiveness of krill oil supplementation on chronic pain and physical function in older adults with chronic musculoskeletal pain. Feasibility will be determined as (1) meeting at least 80% of the recruitment goal, (2) no more than 20% attrition, and (3) treatment acceptance and adherence ( $\geq 70\%$  consumption of prescribed doses and increased blood  $\omega$ -3 index [%EPA+DHA in erythrocytes]).

**Specific Aim 2:** Evaluate the impact of krill oil supplementation on purported physiological changes. Specifically, we will assess the impact of krill oil supplementation on the blood profile of essential fatty acids (i.e.,  $\omega$ -3 index [%EPA+DHA in erythrocytes] and the  $\omega$ -6: $\omega$ -3 ratio) and inflammatory biomarkers.

**Specific Aim 3:** Obtain preliminary evidence of the effectiveness of krill oil supplementation to reduce pain and improve physical function in older adults with chronic musculoskeletal pain.

**Table 1. Objectives and Endpoints**

| Objectives                             | Endpoints   | Justification for Endpoints  |
|--|---|--|
| Primary                         |   |  |
| Feasibility                            | 
 
• ≥80% recruitment
 
• <20% attrition
 
• ≥70% adherence
 
                                 | The pilot will serve as a small-scale study to inform the feasibility of future large-scale trials.                      |
| Secondary                       |   |  |
| Blood profile of essential fatty acids | 
 
• Omega-3 index ≥8%
 
• n-6:n-3 ratio ≥4:1
 
   | The purported physiological change of krill oil supplementation is an increased omega-3 index and reduced n-6:n-3 ratio. |
| Tertiary/Exploratory            |   |  |
| Pain and physical function             | 
 
• 20% pain reduction (0-10 scale)
 
• 1-pt improvement in SPPB
 
• 50-m improvement in 6MWT
 
 | Pain and physical function are the primary endpoints of a future fully powered clinical trial.                           |

## 6. Research Plan:

[figure not shown]
**6.1. Preliminary evidence:** A high plasma  $\omega$ -6: $\omega$ -3 PUFA ratio was associated with increased pain and functional limitations in middle-aged and older adults with chronic knee osteoarthritis. The study consisted of a cross-sectional analysis of 167 participants recruited from the communities surrounding the University of Florida (UF) and the University of Alabama at Birmingham (UAB) as part of the Understanding Pain and Limitations in Osteoarthritic Disease (UPLOAD) cohort. Participants were categorized as having a low or high plasma  $\omega$ -6: $\omega$ -3 ratio based on quartile splits (25th% and 75th%). Those with a high ratio reported greater pain, stiffness, and functional limitations (all  $P < 0.04$ ), and demonstrated lower physical functioning on the Short Physical Performance Battery ( $P = 0.001$ ). On experimental pain measures, those with a high ratio demonstrated higher punctate pain sensitivity at the knee and hand after 10 mechanical taps.

**6.2. Experimental Design:** This pilot will serve as a small-scale study to inform the feasibility of future large-scale trials. Feasibility is measured by metrics that indicate the ability to conduct a large-scale study, such as recruitment of the target population, retention of participants, and adherence to the intervention. This study will utilize a double-blind, randomized, placebo-controlled, repeated measures design to determine the effectiveness of krill oil supplementation on pain and physical function among older adults with chronic musculoskeletal pain (**Fig. 3**). Specifically, the design will determine whether 3 months of supplementation with krill oil will (1) reduce pain intensity and interference, (2) improve physical function, (3) increase plasma  $\omega$ -3 index (%EPA+DHA in erythrocytes) and reduce  $\omega$ -6: $\omega$ -3 ratio, and (4) reduce inflammatory markers. Eligible participants will be randomized on a 1:1 ratio to either krill oil ( $n=20$ ) or placebo ( $n=20$ ). Participants will be instructed to maintain their current dietary habits, including and

especially their consumption of  $\omega$ -3 (e.g., fatty fish) and  $\omega$ -6 PUFAs (e.g., vegetable oils), as well as their current physical activity levels.

**Figure 2. KOPE Study Design**

**6.3. Investigational products:** We will use a commercially available krill oil product (SuperbaBOOST, Aker BioMarine Antarctic US LLC; Metuchen, NJ, USA) which contains 1 g krill oil per capsule (*E. superba* oil; 193 mg EPA, 96 mg DHA, of which 73% of EPA and DHA is bound to phospholipids, 0.11 mg astaxanthin, and 79 mg choline). Participants will be randomly assigned to consume 4 capsules/day of either krill oil (1,288 mg/d EPA+DHA, 0.45 mg astaxanthin, 320 mg choline) or placebo on one occasion with a meal. Placebo capsules will be matched to the krill oil capsules in appearance, odor, and taste, containing 1 g mixed vegetable oil (olive oil, corn oil, palm oil, and medium-chain triglycerides) comprising 31% SFAs, 46% MUFAs, and 22% PUFAs, with no EPA or DHA. This product and dosage have been previously used and found to be well tolerated in older adults.

**6.4. Participants:** The target population of this study will be community-dwelling older adults with chronic musculoskeletal pain and moderate mobility limitations. As shown in **Table 2**, individuals will be eligible based on the following inclusion criteria: (1) age 60 years or older, (2) moderate pain ( $\geq 4$  out of 10) of the hip, knees, or lower back for more than 3 months, (3) demonstrate mobility limitations, and (4) are able and willing to give informed consent. Due to the antiplatelet properties of  $\omega$ -3s, we will exclude anyone with a known coagulation or bleeding disorder, as well as those with a standing regimen of anticoagulants or full-dose aspirin. That said, current evidence does not support an increased risk of bleeding with  $\omega$ -3 supplementation with or without the use of anticoagulants/antiplatelet drugs. Currently, the U.S. Food and Drug Administration (FDA) considers  $\omega$ -3 supplementation up to 5 g/day of EPA+DHA to be safe. In an abundance of caution, we will exclude those with a seafood allergy. Additionally, we will exclude those who have supplemented with  $\omega$ -3 PUFAs in the last 3 months. To ensure enrollment of older adults with low intakes of  $\omega$ -3 PUFAs, we will exclude those who report consuming fatty fish over 2 times per week. The current *Dietary Guidelines for Americans* recommends an intake of at least 8 ounces (i.e., 2 servings) of seafood per week providing ~250 mg/day of EPA+DHA. Lastly, we will exclude anyone with regular use of opioids or high-dose non-steroidal anti-inflammatory drugs within 30 days of randomization.

**Table 2. Inclusion and Exclusion Criteria**

| Inclusion   |
|---|
| 
 
• Provision of signed and dated informed consent form
 
• Stated willingness to comply with all study procedures and availability for the duration of the study
 
• Male or female, aged <math>\geq 60</math> years
 
• Exhibiting chronic musculoskeletal pain of the hip, knees, or lower back (<math>>3</math> months)
 
• Average pain <math>\geq 4</math> on a 0–10 numeric rating scale
 
• Exhibiting moderate mobility limitations (Short Physical Performance Battery score 4-10)
 
• Ability to take oral supplement and be willing to adhere to the supplementation regimen
 
• Agreement to adhere to Lifestyle Considerations (see section 6.4.d) throughout study duration
 
  |
| Exclusion   |
| 
 
• Any known coagulation or bleeding disorders
 
• Standing regimen of anticoagulants or full-dose aspirin
 
• Regular use of opioids or high-dose NSAIDs
 
• Taking medication known to affect muscle (e.g. steroids)
 
• Taking selective serotonin reuptake inhibitors (SSRIs)
 
• Omega-3 supplementation within the past 3 months
 
• High consumption of fatty fish (<math>>2</math> servings/week)
 
• Habitual supplementation with other complementary medicines/supplements that may affect the study results, including St. John's Wort
 
• Known allergy to seafood
 
• Clinically significant conditions: uncontrolled diabetes, severe cardiovascular disease, seizure disorders, uncontrolled hypertension (<math>>150/90</math>mmhg at baseline), cancer or cancer that has been in remission <math><5</math> years
 
• History of atrial fibrillation or atrial flutter
 
• Dementia
 
• History of smoking, alcohol abuse, or illicit drug use
 
• Ambulatory impairments which would limit the ability to perform physical function tests
 
• Treatment with another investigational drug or other intervention within 3 months
 
• Planning a surgical procedure during the study period
 
• Planning to permanently leave the area during the study period
 
 |

**6.4.a. Recruitment:** Our team has substantial experience recruiting older adults with chronic pain and moderate functional impairments. Recruitment efforts will be aided by the UF Older Americans Independence Center's Clinical Research Core. Participants will be recruited from the areas surrounding the University of Florida in Gainesville/Alachua County, Florida. There are  $>284,000$  older adults ( $\geq 65$ y) residing in Alachua County, FL. If needed, recruitment will be expanded to neighboring North/Central Florida regions.

**6.4.b. Screening:** Screening for eligibility will consist of a two-step process, starting with a phone screening to assess basic eligibility criteria. If found eligible via phone screen, interested individuals will be invited to an in-person screening visit. The screening visit will collect demographic characteristics (e.g., age, race/ethnicity, education, income), anthropometric measures, as well as a comprehensive pain history and physical function testing (SPPB) to assess functional status.

**6.4.c. Randomization and blinding:** The trial will use a double-blinded design, so that participants, investigators, and assessors will be blinded to group assignments. Randomization for this study will be conducted using REDCap (Research Electronic Data

Capture), a secure, web-based application designed to support data capture for research studies. REDCap provides automated randomization to ensure unbiased allocation of participants to study groups and audit trails to maintain a detailed log of all randomization activities for transparency and reproducibility. The randomization module in REDCap will be configured to use the random block method, ensuring balanced allocation across groups.

**6.4.d. Lifestyle considerations:** During this study, participants are asked to (1) maintain their current dietary habits, especially their consumption of  $\omega$ -3 (e.g., fatty fish) and  $\omega$ -6 PUFAs (e.g., vegetable oils), (2) maintain current physical activity levels, and (3) not participate in other interventional research studies.

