## **6.5. Assessments (Table 3):**

### **6.5.a. Safety.**

- Vitals. Blood pressure, pulse, and temperature will be obtained at the beginning of every study visit.

Blood chemistry. Blood samples will be collected and used for comprehensive metabolic panel (CMP), complete blood count (CBC), lipid panel, and high sensitivity C-reactive protein (hs-CRP) at baseline and subsequent in-person visits. In case the initial tests are inconclusive or if further analysis is required, the participants may be asked to return for an additional blood draw.

- Adverse events. Participants will be queried about adverse events at every follow-up, including quarterly phone calls and follow-up visits.
- Medical history will be evaluated at screening and updates will be obtained at every visit thereafter.

**6.5.b. Adherence to supplementation protocol.** Remaining capsules will be counted at every follow-up. Adherence will be quantified as the percentage of capsules taken out of those dispensed.

**6.5.c. Common Data Elements (CDEs).** Key sociodemographic characteristics will be obtained at the Screening Visit (e.g., age, sex, race and ethnicity, income).

**6.5.d. Anthropometrics.** Height and weight will be obtained and used to calculate body mass index ( $\text{kg}/\text{m}^2$ ). Height will only be measured at baseline. Weight and waist circumference will be measured at every study visit.

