**6.6.d. Reporting of AEs/SAEs:** Study progress and safety will be reviewed bi-weekly or more frequently by the principal investigator. Progress reports, including AEs will be provided to an Independent Monitoring Committee for bi-annual reviews. The Independent Monitoring Committee for this study will consist of an established board that reviews all studies conducted within the University of Florida's Pepper Center during bi-annual conference calls. This board is comprised of (1) [name]., Chair, epidemiologist, (2) [name]., biostatistician, and (3) [name]., physician/clinical researcher. An annual report will be compiled and will include a list and summary of AEs, and whether adverse event rates are consistent with pre-study assumptions.

The PI will immediately report to the sponsor any SAE, whether or not considered study intervention related, including those listed in the protocol, and must include an assessment of whether there is a reasonable possibility that the study intervention caused the event. All SAEs will be followed until satisfactory resolution or until the site investigator deems the event to be chronic or the participant is stable.

The study sponsor will be responsible for notifying the Food and Drug Administration (FDA) of any unexpected fatal or life-threatening suspected adverse reaction as soon as possible, but in no case later than 7 calendar days after the sponsor's initial receipt of the information. In addition, the sponsor must notify FDA and all participating investigators in an Investigational New Drug (IND) safety report of potential serious risks, from clinical trials or any other source, as soon as possible, but in no case later than 15 calendar days after the sponsor determines that the information qualifies for reporting.

**6.6.e. Reporting events to participants:** In the case that adverse events are identified from blood chemistry tests, participants will be immediately notified by the investigators.

**6.7. Participant discontinuation/withdrawal from the study:** Participants are free to withdraw from participation in the study at any time upon request. The investigators may discontinue or withdraw a participant from the study for the following reasons:

- Significant study intervention non-compliance
- If any clinical adverse event (AE), laboratory abnormality, or other medical condition or situation occurs such that continued participation in the study would not be in the best interest of the participant

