## 7. Possible Discomforts and Risks:

Due to its antiplatelet properties,  $\omega$ -3 supplementation may increase the risk of bleeding at high doses when combined with antiplatelet/anticoagulant medications. Commonly reported side effects of  $\omega$ -3 supplements are usually mild and include unpleasant taste, bad breath, heartburn, nausea, gastrointestinal discomfort, diarrhea, headache, and odoriferous sweat.

The risks associated with the placebo, a mixture of vegetable oils, are similar to those for krill oil, and include upper respiratory tract infections, joint and back pain, gastrointestinal

disorders, and headaches. There is also a potential risk for worsening of cholesterol with the mixed vegetable oil placebo.

There are potential risks associated with the questionnaires, physical function tests, and cognitive tests administered in this study. Questionnaires and cognitive function tests pose a minimal risk of mental fatigue, embarrassment, discomfort, and/or frustration. Physical function tests have an inherent risk of physical discomfort, pain, and/or injury to the participants.

Blood draws carry minimal risks, including pain and/or discomfort, bruising and swelling, excessive bleeding, lightheadedness, and rarely, infection or nerve damage at the puncture site.

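### The bleeding-related drug exclusion rests on an antiplatelet rationale but leaves out standing non-aspirin antiplatelet drugs

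*Protocol*

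**What the plan says.** Section 6.4 of the protocol opens the bleeding-related exclusions with a reason, "Due to the antiplatelet properties of" omega-3s. It then excludes people with a known coagulation or bleeding disorder, "as well as those with a standing regimen of anticoagulants or full-dose aspirin". Table 2 carries the same drug item: "Standing regimen of anticoagulants or full-dose aspirin".

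The next sentence of section 6.4 qualifies the precaution. It says that current evidence does not support a higher bleeding risk from omega-3 supplements, "with or without the use of anticoagulants/antiplatelet drugs". The section then cites an FDA position that up to 5 g/day of EPA+DHA is safe.

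Section 7 describes the hazard in wider terms: supplementation "may increase the risk of bleeding at high doses when combined with antiplatelet/anticoagulant medications".

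The SAP says nothing on eligibility.

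**The concern.** The stated reason for the exclusion is an effect on platelets. Of the two drug classes named in section 7, anticoagulants are excluded in full, while antiplatelet drugs are excluded only when the drug is full-dose aspirin. The non-aspirin members of the class closest to the rationale are left out.

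The result is an odd ordering at screening. A person on full-dose aspirin is turned away. A person on a standing non-aspirin antiplatelet drug, even taken with low-dose aspirin, meets no drug exclusion and can be randomised to krill oil. What is at stake is who is enrolled under a safety precaution.

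**Working it through.** No power, alpha or event figure bears on this point, and the plan gives no figure of its own to reproduce. The main check is a reading of the criteria. The arithmetic only sets the scale.

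**1. Does another criterion close the gap?** Table 2 has 17 exclusion bullets, and none names a non-aspirin antiplatelet drug. The nearest ones are:

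- Coagulation or bleeding disorders: a condition, not drug use.
- Opioids and NSAIDs: NSAIDs count only at high dose.
- SSRIs, atrial fibrillation or flutter, and planned surgery: each lowers bleeding exposure by another route, but none refers to antiplatelet drugs.
- "Clinically significant conditions: uncontrolled diabetes, severe cardiovascular disease, seizure disorders, uncontrolled hypertension": the severe cardiovascular disease item may remove some users, but not those whose disease is not judged severe.

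The gap is narrowed but stays open.

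**2. Does the evidence sentence explain it?** That sentence covers anticoagulants and antiplatelet drugs alike. Taken at face value it would argue for dropping the precaution for both. The protocol keeps it for all anticoagulants and for full-dose aspirin, so the sentence does not account for the split.

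**3. How does the dose compare with the level cited as safe?** Section 6.3 gives 193 mg EPA and 96 mg DHA per capsule, 4 capsules a day, and a stated daily total of 1,288 mg.

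- From capsule contents: 4 × (193 + 96) = 1,156 mg/d; 1,156 / 5,000 = 23.1%.
- As stated: 1,288 / 5,000 = 25.8%.

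Either way the dose is about a quarter of 5 g/day.

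**4. How many people might be involved?** The documents give no prevalence, so let p be the assumed share of otherwise eligible people on a standing non-aspirin antiplatelet drug. There are 20 people in the krill arm, 40 in total, and 32 at the 80% recruitment mark.

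| Quantity | Formula | p = 2% | p = 5% | p = 10% |
|---|---|---|---|---|
| Expected users in krill arm | 20p | 0.4 | 1.0 | 2.0 |
| Chance of at least one in that arm | 1 − (1 − p)^20 | 33% | 64% | 88% |
| Extra otherwise eligible people needed to randomise 40 | 40/(1 − p) − 40 | 0.8 | 2.1 | 4.4 |
| Extra needed to reach 32 | 32/(1 − p) − 32 | 0.7 | 1.7 | 3.6 |

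The first two rows measure exposure (whether a user would be enrolled), not the chance of a bleed. The last two rows are the recruitment cost of the fix.

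**The case against.** The strongest reply is that this is sponsor judgement. Section 7 is a risk disclosure, not an eligibility rule, and it limits the risk to high doses. The documents do not call the study dose high. Section 6.4 shows that the sponsor had antiplatelet drugs in view when it set the exclusion, and it presents the exclusion as going beyond the evidence. Where to stop such a precaution is a choice. Other safeguards also apply: the exclusions above, the CBC, adverse event queries, and the rule that "Medical history will be evaluated at screening and updates will be obtained at every visit thereafter".

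Much of this stands, and it rules out some stronger readings:

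- A reader might infer that Table 2 contradicts section 7, or that the trial is unsafe for these people. The documents support neither, because the risk in section 7 is conditional on high doses and no bleeding rate is given.
- A reader might take the evidence sentence as proof that there is no added bleeding. It says only that current evidence does not support an increase.
- A reader might see a second gap in section 6.7, since starting such a drug mid-study would not count as meeting an exclusion criterion. Section 6.7 refers back to the same list, and its reasons are discretionary: "The investigators may discontinue or withdraw a participant from the study for the following reasons". They include the participant's best interest. It is not a separate fault.

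It can also be said that allowing low-dose aspirin leaves the criterion narrower than section 7 even after the change. That is true. But the qualifier on aspirin dose suggests that the sponsor drew that line on purpose. Nothing in the text suggests the same for the other antiplatelet drugs.

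The reply does not explain why one class is excluded in full and the other only in part. Monitoring can detect a bleed, but it does not decide who is enrolled.

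**Conclusion.** The point holds as an internal mismatch in a precaution that the sponsor chose to take. The exclusion is justified by an antiplatelet effect, yet it does not reach standing non-aspirin antiplatelet drugs, and no other criterion fully does so. The documents do not show whether the omission was deliberate.

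Absolute risk is low, given the dose, the protocol's reading of the evidence and the other exclusions. Excess bleeding cannot be estimated from the documents. The 2% to 10% prevalence range is an assumption and should carry no weight as evidence of harm. This is a cheap safety improvement to consider, not a defect that affects the trial's conclusions.

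**What to change.** In Table 2 and section 6.4, reword the criterion to: *Standing regimen of anticoagulants, non-aspirin antiplatelet drugs, or full-dose aspirin*. Leave low-dose aspirin alone permitted. Ask about these drugs at both the phone and the in-person screening in section 6.4.b. Apply the change to new screenings. The investigator can review anyone already randomised who takes such a drug, using the discretion that section 6.7 already gives.

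The cost is a one-line amendment and about 1 to 5 extra screen failures (0.8 to 4.4 before rounding up) under the assumed 2% to 10% prevalence. That could slow recruitment slightly, which matters a little because recruitment is a primary feasibility measure.
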